The primary purpose of the current proposal is to obtain preliminary data to increase the likelihood of funding for a future NIH grant, while balancing the feasibility of completing the current proposal. To that end, we will utilize a within-subject, repeated measures design to assess the feasibility of administering pioglitazone for four weeks to non-treatment and treatment-seeking individuals with AUD and elevated levels of stress/anxiety (**N=20**). Participants will undergo pre- and post-treatment human laboratory assessment of stress-reactivity and stress-induced alcohol craving. During treatment, changes in alcohol use, stress/anxiety, and alcohol craving will be assessed in the natural environment. The study design features 1) rigorous monitoring of medication compliance (Medication Event Monitoring System (MEMs)) and alcohol use (urinary ethyl glucuronide (ETG)); 2) biological assessment of stress reactivity (salivary cortisol, blood pressure, and heart rate); and 3) a multi-dimensional assessment of stress-induced alcohol craving incorporating both traditional measures of alcohol craving in addition to relatively novel behavioral economic measures (delay discounting, alcohol demand). Taking these measures together, we hope to present a robust and comprehensive characterization of pioglitazone on alcohol use, stress reactivity, and stress-induced alcohol craving.

SPECIFIC AIMS

Specific Aim 1: To assess pre- to post-treatment reductions in stress reactivity (self-report, salivary cortisol, heart rate, blood pressure) and stress-induced alcohol craving (self-report, alcohol demand) in the human laboratory setting.

Hypothesis 1: *We will observe pre- to post- treatment reductions in stress reactivity and stress-induced alcohol craving.*

Specific Aim 2: To assess changes in alcohol drinking (drinks per day, heavy drinking days), stress/anxiety (PSS, HAMA, PCL-5), and alcohol craving (PACS, delay discounting, alcohol demand) during treatment in the natural environmental setting.

Hypothesis 2: *We will observe decreased alcohol drinking, stress/anxiety, and alcohol craving over the course of treatment.*

There is increasing attention and evidence supporting the potential role of the PPAR γ system as a novel target in the treatment of AUD. From a translational perspective, this study is timely and likely to advance our understanding of stress as a mechanism of action of pioglitazone effects.

IRB NUMBER: HSC-MS-18-0922

BACKGROUND AND RATIONALE

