baseline stress reactivity assessment. Individuals will be excluded for exhibiting severe scores on the HAM-A, PSS, BDI-II, or PTSD checklist (PCL-5) at the discretion of the admitting physician ([name]); physical dependence on alcohol; greater than mild substance use disorder on drugs other than alcohol, nicotine, and marijuana; contraindications for taking pioglitazone; medical conditions contraindicating pioglitazone pharmacotherapy or taking contraindicated medications; be pregnant, nursing, or planning on becoming pregnant during the course of the study; have any other illness, condition, or use of medications, which in the opinion of the PI and/or admitting physician would preclude safe and/or successful completion of the study. Recruitment strategies will include local advertising in print media, public service announcements on radio, and referrals to CNRA in the Houston metropolitan area.

Baseline Screening. Participants will receive a comprehensive medical and psychiatric evaluation including: a medical-history questionnaire, physical examination, laboratory chemistries (e.g., blood chemistry screen, complete blood count, urinalysis and urine pregnancy test), and ECG. Clinicians will conduct the **SCID**, the **ASI ASI**⁴⁹, the **KMSK**⁵⁰ assessment of lifetime substance use interview, and **TLFB**⁵¹. Alcohol dependence will be assessed using the SCID and the **CIWAA**⁵².

Alcohol-Related Measures. Assessment of alcohol use will include self-report (**TLFB**), **BrAC** (Alco-Sensor FST, Intoximeters, Inc., Saint Louis, MO). Severity of alcohol use will be assessed using the **AUDIT**⁵³. **Motivation to quit** will be assessed using the Alcohol Ladder questionnaire. **Alcohol craving** will be assessed using a 5-item questionnaire⁵⁷. ETG will be assessed using dipcards with a 300 ng/ml cutoff. ETG dipcards show good agreement with traditional immunoassays⁵⁸⁻⁶⁰.

Behavioral Economic Measures. Alcohol demand will be assessed via the **Brief Assessment of Alcohol Demand** (BAAD)⁴², a 3-item questionnaire measuring the three most common indices of alcohol demand. **Delay discounting** will be assessed for both money and alcohol using a computerized task at weekly clinic visits developed by [name] (PI)^{61,62,71,63-70}.

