Natural Environment Procedures (Specific Aim 2). At Study Week 0, all participants will receive a pamphlet copy of the “Rethinking Drinking: Alcohol and Your Health” providing research-based information related to alcohol use (RethinkingDrinking.niaaa.nih.gov). Research staff will go over the pamphlet’s information with the participant at the initial visit and subsequent visits as necessary. At each study visit, participants will receive study medication for the week and assessed for adverse events and medication compliance. At each visit, participants will also be assessed for recent alcohol use (self-report, ETG, BrAC), alcohol craving (PACS), and stress/anxiety (HAM-A, PSS). At the end of the study, participants will be referred to local alcohol treatment services as needed.

Participant Payment & Compensation. Participants will receive be able to receive \$300 for completing the study (\$50 for completing baseline screening; \$25 for each visit (\$100); \$25 for stress reactivity assessments (\$50); and \$100 completion bonus). Additionally, participants will potentially receive \$10/week (up to \$40) for demonstrating medication compliance. Participants will also receive parking/bus fare compensation at each visit worth \$5.

DATA ANALYSIS PLAN

General Data Analytic Strategy. Analyses will proceed in parallel using frequentist and Bayesian statistical inference. Frequentist analyses will examine relationships between predictors and outcomes using traditional measures of effect size and statistical significance (i.e., regression coefficients, standard errors,

confidence intervals, and p -values), while Bayesian analyses will measure uncertainty in model parameter estimates via posterior distributions and directly evaluate the probability of the alternative hypothesis.

Specific Aim 1: assess pre- to post-treatment reductions in stress reactivity (self-report, salivary cortisol, heart rate, blood pressure) and stress-induced alcohol craving (self-report, alcohol demand) in the human laboratory setting.

Hypothesis 1: We will observe pre- to post- treatment reductions in stress reactivity and stress-induced alcohol craving. Generalized linear mixed modeling will be used to evaluate each outcome as a function of time (pre-test and post-test) in unique models.

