Specific Aim 2: Demonstrate reduced alcohol drinking (drinks per day, heavy drinking days), stress/anxiety (PSS, HAMA, PCL-5), and alcohol craving (PACS, delay discounting, alcohol demand) during treatment in the natural environmental setting.

Hypothesis 2: We will observe decreased alcohol drinking, stress/anxiety, and alcohol craving over the course of treatment. Generalized linear mixed modeling will be used to evaluate each outcome as a function of time in unique models. Alcohol consumption will be modeled via drinks per drinking day, such that the number of positive drinking episodes a participant experienced in a week will be included as a count outcome (i.e., Poisson-distributed) and the number of drinking days in a week will be controlled for as an off-set covariate.

Power/Sample Size Considerations. The frequentist framework using null hypothesis statistical testing can provide some understanding of changes over time for each outcome. However, in evaluating a small within-subjects pilot trial of $N = 20$ participants, Bayesian statistical inference provides a superior framework for deriving evidence regarding the magnitude and direction of change over time for each model. The posterior probability of each effect would then be useful to inform effect sizes for power calculations and/or prior distributions in future research. As due diligence, however, a conventional frequentist power analysis follows. For the current proposal, power estimates are calculated using G*Power 3.1.9.2 and focus on reduction in alcohol consumption. Assuming alpha = 0.05 (one-tailed), an average baseline rate of 10.5 drinks/week across all participants (averaged between 14 and 7 drinks/week for male and female participants, respectively), a sample size of $N = 20$ participants provides 80% power to detect a 20% decrease in alcohol consumption over five weeks.

REFERENCES

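### The alcohol consumption model contradicts its own definition and, with drinking days as the offset, estimates neither Aim 2's drinks per day nor the drinks per week used for power

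*Combined protocol and SAP*

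**What the plan says.** Specific Aim 2 names the drinking outcomes: "To assess changes in alcohol drinking (drinks per day, heavy drinking days". The same two outcomes are repeated when the aim is restated in the Data Analysis Plan.

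Under Hypothesis 2, mixed models will "evaluate each outcome as a function of time in unique models". One consumption model is spelled out, in a single sentence with three parts:

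- the measure: "Alcohol consumption will be modeled via drinks per drinking day"
- the Poisson outcome: "the number of positive drinking episodes a participant experienced in a week will be included as a count outcome"
- the denominator: "the number of drinking days in a week will be controlled for as an off-set covariate"

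The plan does not define an episode. It gives no rule for a week without drinking and no form for the heavy-drinking-days model. Power/Sample Size Considerations uses a third scale, "an average baseline rate of 10.5 drinks/week across all participants", and claims 80% power for a 20% decrease.

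**The concern.** The named measure needs drinks in the numerator, but the stated numerator counts episodes. The sentence therefore cannot be programmed without guessing what was meant.

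Correcting the numerator to drinks leaves a second problem. Dividing by drinking days removes drinking frequency from the result. A participant who goes from five drinking days to two at the same intake per day shows no change, and one who stops altogether contributes undefined weeks. These are among the best responses the hypothesis could hope for.

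The study's stated product is effect estimates for planning later research. The estimate from this model would not be the consumption effect named in the aim or in the power statement. Fitting the same model in Bayesian form does not change what it estimates.

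**Working it through.** **1. The plan's own power figure.** The inputs from Power/Sample Size Considerations are N = 20, one-sided alpha 0.05, 10.5 drinks/week and a 20% fall. The test is not stated. I assume Poisson weekly drink counts at Weeks 0 to 4, with a log-linear trend reaching 0.80 at Week 4.

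- Slope b = ln(0.8)/4 = -0.0558; weekly mean at week k = 10.5 × 0.8^(k/4).
- Information at this slope = 20 × [Σk²μ − (Σkμ)²/Σμ] = 20 × (261.8 − 168.0) = 1,876, so SE = 0.0231.
- Information under no change = 20 × 10.5 × 10 = 2,100, so SE = 0.0218.
- Power = Φ[(0.0558 − 1.645 × 0.0218)/0.0231] = 80.6%. Using 0.0231 throughout gives 78.0%.

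On this assumed design the stated 80% is recovered, with weekly drinks as the outcome, no drinking-day offset and no overdispersion. Other designs give other values: 70-73% for one week before and one after, and 88-89% for Week 0 against four weeks at 0.80.

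**2. What each reading estimates.** Weekly drinks = drinking days × drinks per drinking day, so the weekly ratio is the product of a frequency ratio and a quantity ratio.

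| Count | Drinking days used as | Time effect |
|---|---|---|
| Episodes, one per drinking day | log offset | 1.00 always |
| Drinks | log offset | quantity ratio only |
| Drinks | ordinary covariate | change in drinks at a fixed number of drinking days |

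No row gives drinks per day or per week. The direction can even reverse: 5 days × 2.1 drinks becoming 3 × 2.8 takes weekly drinks from 10.5 to 8.4 (ratio 0.80), while drinks per drinking day has ratio 2.8/2.1 = 1.33.

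**3. Size, in an assumed illustration.** Baseline is 3 days × 3.5 drinks = 10.5 per week, where 3.5 is the midpoint of the 3 and 4 drinks-per-occasion limits in Participants, Recruitment, and Setting. Drinking days are binomial out of 7. Drinks on a drinking day are 1 + Poisson with mean 2.5 extra drinks (between-person log-SD 0.4). The analysis is a subject fixed-effect Poisson model of Week 0 against Weeks 1-4 with cluster-robust standard errors. Ranges cover three levels of between-person spread in frequency; differences of a few points are simulation error.

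| 20% weekly fall through | Calendar-day offset: ratio, power | Drinking-day offset (drinks): ratio, power |
|---|---|---|
| (a) fewer days (3 to 2.4) | 0.80, 47-52% | 1.00, about 5% |
| (b) fewer drinks per drinking day (3.5 to 2.8) | 0.80, 50-55% | 0.80, 93-94% |
| (c) equal split | 0.80, 48-54% | 0.90, 47-49% |

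Rejection under no change was 5.7-6.1% (calendar-day) and 4.6-5.4% (drinking-day). In (a), a separate heavy-day model (4 or more drinks assumed) gives a ratio of about 0.8 with 29-31% power.

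**4. Abstinent weeks.** Suppose 1, 2 or 4 of 20 participants abstain in Weeks 2-4 and the rest do not change. Then 3, 6 or 12 of 80 post-baseline person-weeks (4%, 8%, 15%) have log(0) as offset. Weekly drinks fall by the same 4%, 8% or 15%, while the drinking-day-offset ratio stays at 1.00.

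**5. Dispersion of weekly totals on the step 3 inputs.** Variance = 3 × 2.5 + 7 × (3/7) × (4/7) × 3.5² = 7.5 + 21.0 = 28.5 against mean 10.5. The ratio is 2.71 and its square root 1.65. Plain Poisson standard errors would be too small by that factor, and a one-sided 5% test would reject with probability P(Z < −1.645/1.65) = 16% under no change. This bears on how the replacement model is fitted; it is not a further fault in the plan.

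**The case against.** The word for episodes may simply be a slip for drinks, since the sentence opens by naming drinks per drinking day. That is plausible and would remove the contradiction, but not the mismatch with the aim.

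The promise of a separate model for each outcome could be read to include a drinks-per-day model. The plan spells out no such model, and its explicit sentence on how consumption will be modelled points the other way. A heavy-drinking-days model is implied and would register part of a fall in frequency, and ETG and BrAC are also collected. So the blindness to frequency belongs to this one model, not to every outcome in the study.

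The power figures depend heavily on assumptions. With 5 days × 2.1 drinks, or with strongly overdispersed daily drinks, calendar-day power runs from about 32% to 83%. Under the first split fewer than 1% of weeks are drink-free; under the second, power in case (b) with the drinking-day offset drops to about 44%. This stands: the figures illustrate and do not predict. The ratio of 1.00 in case (a) needs none of them.

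Finally, this is a 20-person pilot with no named primary outcome, where power is offered as due diligence. That limits the weight of the drinks-per-week mismatch. It does not excuse a misdefined effect in a study meant to supply effect sizes. Drinks per drinking day is a legitimate measure, but it is not the one the aim states.

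**Conclusion.** The concern holds and should be fixed before analysis. The sentence contradicts itself, and on each reading the specified model misses both the aim's drinks per day and the power statement's drinks per week. With drinks as the count, any fall that comes only from fewer drinking days appears as a ratio of 1.00; this is algebra and depends on no assumed input. If an episode is a drinking day, the ratio is 1.00 under every pattern of change. Abstinent weeks are undefined if drinking days enter as a log offset. If they enter as an ordinary covariate those weeks can stay in, but the time effect remains conditional on frequency. The power contrasts (about 5% against 47-52% for a pure frequency fall, and 93-94% against 50-55% the other way for a pure quantity fall) rest on the assumed 3 × 3.5 split, the daily distribution and the Week 0 against Weeks 1-4 contrast.

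**What to change.** Rewrite the Hypothesis 2 consumption model as follows.

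- **Outcome and offset:** total standard drinks in the week from self-report, with the log of calendar days observed as the offset. The time effect is then a ratio of drinks per day, which equals the weekly ratio when each week is fully observed. Abstinent weeks remain as zeros.
- **Dispersion:** check for and allow overdispersion, for example with a negative binomial model or robust standard errors.
- **Heavy drinking days:** specify the model as heavy days out of days observed.
- **Drinks per drinking day, if kept:** define the count as drinks, label the result as conditional on drinking, and state how zero-drinking weeks are handled.

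The cost is SAP wording. Alcohol-Related Measures states "Assessment of alcohol use will include self-report", and Natural Environment Procedures adds "At each visit, participants will also be assessed for recent alcohol use (self-report, ETG, BrAC". The plan's own drinking-day and heavy-day counts already need day-level records. Intervals will be somewhat wider. If the effect is purely on drinks per drinking day, power is lower than with the planned offset (about 50-55% against 93-94% in the illustration), which is a reason to keep that measure as a labelled secondary.

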Human Laboratory Procedures (Specific Aim 1) Stress-Reactivity Assessment (Salivary Cortisol, HR, BP, Craving) Alcohol Demand, Alcohol Ladder	X				X
Natural Environment Procedures (Specific Aim 2) Alcohol Use and Craving (Self-Report, BrAC, ETG, PACS) Stress and Anxiety (HAM-A, PSS, BDI-II, PCL-5) Delay Discounting, Alcohol Demand	X	X	X	X	X
Natural Environment Procedures (Specific Aim 2) Alcohol Use and Craving (Self-Report, BrAC, ETG, PACS) Stress and Anxiety (HAM-A, PSS, BDI-II, PCL-5) Delay Discounting, Alcohol Demand	X	X	X	X	X

SCID - Structured Clinical Interview for DSM-5; **ASI** - Addiction Severity Index⁴⁹; **KMSK** - Kreek-McHugh-Schluger-Kellogg scale⁵⁰; **TLFB** - Timeline Followback⁵¹; **CIWAA** - Clinical Institute Withdrawal Assessment for Alcohol⁵²; **AUDIT** - Alcohol Use Identification Test⁵³; **BrAC** - Breath Alcohol Concentration; **ETG** - Ethyl Glucuronide; **PACS** - Pennsylvania Alcohol Craving Scale⁵⁴; **HR** - Heart Rate; **BP** - Blood Pressure; **HAM-A** - Hamilton Anxiety Rating Scale⁵⁵; **PSS** - Perceived Stress Scale⁵⁶; **PCL-5** - PTSD Checklist for DSM-5; **BDI-II** - Beck Depression Inventory - II.

Participants, Recruitment, and Setting. Participants (**N=20**) will consist of non-treatment and treatment-seeking individuals diagnosed with AUD (DSM-5) between 21 to 40 years old and fluent in English; past month excessive alcohol use (>7 drinks/week for women, >14 drinks/week for men, >3 drinks/occasion for women>4 drinks/occasion for men)¹⁴; baseline HAM-A or PSS Score indicative of mild to moderate anxiety (score 8 to 23) or moderate stress (score 14 to 26), respectively; and increase in alcohol craving following the

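### The Aim 2 drinking model fixes its variance at the Poisson value with no dispersion term or check, so its error rate can miss 5% in either direction, and the variance behind the 80% power is not stated

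*Combined protocol and SAP*

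**What the plan says.** Under Specific Aim 2 in the Data Analysis Plan, the general statement is "Generalized linear mixed modeling will be used to evaluate each outcome as a function of time in unique models". No random-effect structure is given. For alcohol, the target is drinks per drinking day. The count is described as "the number of positive drinking episodes a participant experienced in a week", it is to be "included as a count outcome (i.e., Poisson-distributed", and "the number of drinking days in a week will be controlled for as an off-set covariate". Nothing in the plan allows the variance to differ from the mean or provides for checking whether it does.

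Power/Sample Size Considerations is on a different scale. It starts from "an average baseline rate of 10.5 drinks/week across all participants", adds "Assuming alpha = 0.05 (one-tailed", and concludes that 20 participants "provides 80% power to detect a 20% decrease in alcohol consumption over five weeks". It names the software (G*Power) but no test family, SD, variance or within-person correlation. The same paragraph presents this power as a supplement to the preferred Bayesian analysis, and says the posterior results should feed effect sizes and priors in later research.

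The entry criteria (Participants, Recruitment, and Setting) set past-month limits of more than 7 and 14 drinks a week for women and men, and ">3 drinks/occasion for women>4 drinks/occasion for men".

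**The concern.** A Poisson likelihood sets the week-to-week variance within a person equal to the mean. A random intercept absorbs stable differences between people, not extra scatter from one week to the next. If the counts scatter more than Poisson, standard errors are too small, intervals too narrow, and noise is declared a fall in drinking too often. If they scatter less, the test is conservative and loses power.

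This matters more than usual here for two reasons. Alcohol consumption is the only outcome with a stated power. And a Bayesian model on the same likelihood carries the same misplaced precision into the posteriors that the plan intends to pass on to future power calculations and priors.

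**Working it through.** **1. The plan's own figure.** Inputs from the power paragraph: N = 20, 10.5 drinks/week, rate ratio 0.80, one-sided 0.05. The test is not named, so a within-person log-linear Poisson trend is one candidate.

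- Slope = ln(0.80)/(number of points − 1). Information = 20 × Σ μ_t (t − t̄)², where μ_t is the expected weekly count and t̄ is the μ-weighted mean week.
- Five points (Weeks 0 to 4): slope −0.0558, SE 0.0231, z = 2.42, power = Φ(2.42 − 1.645) = 78%.
- Six points (five intervals): slope −0.0446, SE 0.0174, z = 2.56, power = 82%.

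These bracket 80%. Other Poisson readings do not: a paired pre/post comparison gives about 70%, Week 0 against Weeks 1 to 4 gives 88%, and two-group Poisson regression gives 49% to 97% depending on exposure. The stated figure is therefore consistent with a Poisson trend, but not confirmed as one.

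**2. Size of the planned test, with the offset.** Given the number of drinking days, the variance/mean ratio of the weekly count is r = SD²/mean of drinks per drinking day. The error of a nominal one-sided 5% test is then 1 − Φ(1.645/√r). The documents give neither the mean nor the SD, so both are assumed. The formula column uses a mean of 4.5. The simulations used 20 people, five weeks, person effects and a linear week term, with means of 4 to 5.

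| Drinks per drinking day (assumed) | r | Formula | Simulation |
|---|---|---|---|
| Fixed | 0 | 0% | 0% |
| 1 + Poisson | 3.5/4.5 = 0.78 | 3.1% | 3.0% |
| Poisson | 1 | 5.0% | 5.3% |
| SD 2.5 | 6.25/4.5 = 1.39 | 8.1% | 8% |
| SD 3 | 9/4.5 = 2.00 | 12.2% | 12% |
| SD 3.5 | 12.25/4.5 = 2.72 | 15.9% | 15% |

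At SDs of 3 and 3.5, nominal 95% intervals covered about 84% and 78% in simulation.

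**3. The same test with person-clustered errors.** With the offset kept and a t reference on 19 degrees of freedom, the simulated one-sided error was 4.9% to 5.6% in every case but fixed quantity. That case leaves no residual scatter, and the test stayed near 0%.

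**4. Power on drinks per week.** Here there is no offset to absorb variation in drinking days. Suppose 80% rests on Poisson variance and the true variance is φ times the mean. Power with correct errors is then Φ((1.645 + 0.842)/√φ − 1.645):

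- φ = 2: Φ(1.758 − 1.645) = 55%
- φ = 3: Φ(1.436 − 1.645) = 42%
- φ = 4: Φ(1.243 − 1.645) = 34%

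**5. Power and model are on different outcomes.** In simulation (3 and 4 drinks per drinking day for women and men, Poisson daily quantity), the offset model detected a 20% fall 76.6% of the time when it came from fewer drinks per drinking day. When it came only from fewer drinking days, detection was 4.9%. A power figure on drinks per week does not carry over to the planned test.

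**The case against.** The strongest objection is that the offset already deals with bout drinking. This is largely right, and it rules out a stronger reading that a reader might infer from the entry limits. That reading goes as follows. Women at 7 drinks a week in bouts of 4 have 1.75 drinking days, so with binomial days the ratio is 4 × (1 − 0.25) = 3.0. Men at 14 in bouts of 5 have 2.8 days, giving 5 × (1 − 0.40) = 3.0. A ratio of 3 puts the one-sided error at 1 − Φ(1.645/1.732) = 17%, and more variable bouts take it to about 20%.

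The documents do not support this, for two reasons. The extra variance comes from the random number of drinking days, which is exactly what the offset conditions on; under this mechanism the planned test runs at about 5% or below. And the limits are thresholds for entry, not typical values. Taking them as typical (3 and 4 per occasion) gives anything from 2 to 5, depending on assumptions that the documents do not supply.

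Three further objections have force:

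- If the outcome is literally a count of episodes, the amount drunk per bout does not enter it. Episodes given drinking days would tend to vary less than Poisson, so the error would be on the conservative side.
- The inflated rows in the table depend on assumed SDs.
- The plan does not say that its power uses Poisson variance, and it gives that power only as a supplement in a 20-person pilot.

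What remains is that the offset protects the test only if daily quantity is close to Poisson, and the plan neither argues for this nor checks it.

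**Conclusion.** The point holds in a limited form. The plan fixes the variance by assumption, and the size of the resulting error is unknown in both magnitude and direction: from near 0% to about 15% for a nominal one-sided 5% test, over a fixed daily quantity up to an SD of 3.5 around a mean of 4 to 5. These figures assume five weekly points, no dropout, and a one-sided test at the level used in the power paragraph. They are a range, not a prediction.

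The overstatement of power is conditional. If the 80% rests on Poisson variance, and weekly drinks vary more than Poisson, it is too high, by an amount that depends on a ratio the documents do not give. No single figure can replace it on the present information.

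This should be changed, since the remedy is cheap and works whichever way the variance departs from Poisson. It is not a demonstration that the planned test is anti-conservative.

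**What to change.** - **Outcome.** State whether the count is drinks or episodes, and keep the drinking-day offset if the target is drinks per drinking day.
- **Frequentist test.** Use person-clustered (sandwich) standard errors with a t reference on 19 degrees of freedom. This corrects for too much or too little scatter.
- **Bayesian model.** Use a likelihood with a free dispersion parameter, either negative binomial or Poisson with an observation-level random effect. Both handle over-dispersion only, so report a dispersion check beside them.
- **Power.** State the test family and variance behind the 80%. Then restate power over a range of dispersion values for the outcome actually modelled, without substituting one new figure.

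The cost is a few sentences in the analysis plan, one re-run of the power calculation and a little more analysis work. The stated power will probably look less favourable. No extra participants or data are needed.

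### The only alcohol-consumption model takes drinking days as its Poisson exposure, so it drops abstinent weeks and ignores falls in drinking days, and does not match Aim 2 or the power statement

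*Combined protocol and SAP*

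**What the plan says.** Specific Aim 2 is stated as: "To assess changes in alcohol drinking (drinks per day, heavy drinking days" and further stress and craving measures. The Data Analysis Plan repeats the drinking outcomes as "reduced alcohol drinking (drinks per day, heavy drinking days". For the models it says: "Generalized linear mixed modeling will be used to evaluate each outcome as a function of time in unique models". Consumption is then given its own sentence, which opens: "Alcohol consumption will be modeled via drinks per drinking day". The outcome of that model is described as follows: "the number of positive drinking episodes a participant experienced in a week will be included as a count outcome (i.e., Poisson-distributed". For the exposure, the sentence ends by stating that "the number of drinking days in a week will be controlled for as an off-set covariate".

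The Power/Sample Size paragraph is on another scale. It takes "an average baseline rate of 10.5 drinks/week across all participants", with "Assuming alpha = 0.05 (one-tailed" test), and claims 80% power with 20 participants for a 20% decrease over five weeks.

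Recent alcohol use is assessed at every visit (Natural Environment Procedures), so weeks without drinking will be observed. The plan does not say how they enter the consumption model: it has no hurdle or zero-inflated part and no alternative exposure such as days observed.

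**The concern.** The offset in a log-link Poisson model is the log of the exposure. If the exposure is the number of drinking days, a fully abstinent week has count 0, exposure 0 and an undefined offset. Software either stops or deletes the row. The parallel Bayesian analysis does not avoid this: a count of 0 with exposure 0 has probability 1 whatever the parameters, so the week carries no information.

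The second consequence is wider. Dividing by drinking days removes from the estimate any reduction achieved by drinking on fewer days, whether or not a whole week is abstinent. The hypothesis is that drinking decreases, and the sample includes treatment-seeking participants who all receive advice on drinking, so fewer drinking days is a foreseeable response.

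At stake is the estimate the pilot exists to supply. The plan wants its posteriors to inform effect sizes and priors for later research. An estimate of drinking intensity alone, read as change in consumption, would carry the wrong quantity forward.

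**Working it through.** **1. The plan's own power figure.** Inputs from the Power/Sample Size paragraph: N = 20, one-sided alpha 0.05, 10.5 drinks/week, 20% decrease. The G*Power procedure is not named, so a Poisson log-linear trend over Weeks 0 to 4 is assumed, with no overdispersion and no variation in slope between participants.

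- Slope: b = ln(0.80)/4 = -0.0558 per week.
- Expected drinks per week over 20 people: 210 at Week 0, falling to 168 at Week 4.
- Standard error at the baseline rate: SE0 = sqrt(1/(210 × 10)) = 0.0218, where 10 is the sum of squared deviations of Weeks 0 to 4.
- Standard error under the alternative: SE1 = 0.0231.
- Power = Phi((0.0558 - 1.645 × 0.0218)/0.0231) = Phi(0.86) = 80.6%. With SE0 at the mean rate it is 78.1%.

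The stated 80% is therefore reproduced, under that assumed procedure, for total drinks per week. On that scale an abstinent week is a valid zero.

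**2. What the specified model estimates.** Taking the numerator to be drinks:

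drinks per week = drinking days per week × drinks per drinking day.

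The Week 4 to Week 0 ratio of weekly drinks is thus the ratio of days times the ratio of intensity. With log(drinking days) as offset, the time coefficient estimates the intensity ratio only.

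- Five drinking days falling to one at 3.5 drinks per day: weekly drinks fall from 17.5 to 3.5, which is 80%. The intensity ratio is 1. In simulation the offset model estimated a change of about 1%, with no rows lost.
- A share q of participants abstinent at Week 4, others unchanged: mean weekly drinks fall by q. The intensity ratio is again 1.

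**3. The abstinent week.** log(0) is minus infinity. A Poisson GLM given four weeks, one with 0 drinks and 0 drinking days, stopped with an invalid-value error and fitted only after that row was deleted.

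**4. Size, under assumed abstinence.** The documents give no frequency of abstinent weeks, so a range is shown. Set-up: 20 people, 5 weeks, 3 drinking days at 3.5 drinks (3 × 3.5 = 10.5 per week), intensity constant, probability of an abstinent week rising linearly from 0 to q at Week 4. Expected rows lost = 20 × q × (0 + 0.25 + 0.5 + 0.75 + 1) = 50q. Poisson regression with subject intercepts, 300 replicates:

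| q | Rows lost of 100 | Estimated fall, offset log(drinking days) | Estimated fall, offset log 7, all weeks |
|---|---|---|---|
| 20% | 9.9 | -0.1% | 19.8% |
| 30% | 14.8 | 0.2% | 28.6% |
| 50% | 25.4 | 0.2% | 50.2% |

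A second simulation (about 4 drinking days at 2.625 drinks, also 10.5 per week; GEE Poisson; one-sided 0.05) gave rate ratios of 1.00 for the drinking-day offset, with rejection in 7%, 6% and 6% of trials. For drinks per week the ratios were 0.79, 0.70 and 0.51, with rejection in 42%, 64% and 94%.

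**5. Is the estimate biased on its own scale?** With a true 20% fall per drinking day and abstinent weeks, unrelated to intensity, rising to 20%, 30% or 50% and dropped, the offset model estimated 19.5%, 20.0% and 20.0%. It recovers the intensity change. Weekly drinking in the first case falls by 1 - 0.8 × 0.8 = 36%, so part of the response is seen and part is not.

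**6. The covariate reading.** If drinking days are entered unlogged with a free coefficient, zero weeks no longer fail. In a separate run of the step 4 set-up the estimated falls were 7.8%, 11.3% and 18.3%, against 20.1%, 27.4% and 48.5% with all weeks and offset log 7. That model adjusts for part of the response.

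**The case against.** Several stronger readings are tempting, and the documents do not support them.

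- **A reader might infer that abstinent weeks are lost from the whole analysis.** They are not. Each outcome has its own model, and heavy drinking days is listed separately; an abstinent week can enter there as 0.
- **A reader might take the 0% against 20-50% contrast as bias from deleted rows.** In those simulations drinks per drinking day truly does not change, so 0% is the right answer on that scale. The comparator estimates a different quantity. Step 5 shows no material bias when abstinence is unrelated to intensity; abstinence related to intensity might cause some, but this was not examined.
- **A reader might conclude that the model shows no change however large the fall.** That requires unchanged drinks per drinking day. A mixed response is partly detected.

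It is also fair to say that drinks per drinking day is a legitimate measure of intensity, that the frequency of abstinent weeks is unknown, that the log-offset reading is not certain because the plan also calls the term a covariate, and that this is a 20-person pilot for preliminary data. These points limit the severity.

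They do not remove the problem. The plan gives no zero-week rule, and its only consumption model estimates neither drinks per day nor drinks per week. The covariate reading does not help (step 6). The same sentence also counts drinking episodes rather than drinks; if an episode is a drinking day, outcome and offset nearly coincide and the rate is about 1 by construction. That is a related fault in the same sentence, and putting the numerator right leaves this one in place.

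**Conclusion.** The point holds for the alcohol-consumption model. Followed as written, it fails on or drops weeks without drinking and gives no credit for fewer drinking days, while Aim 2 and the power statement concern scales on which both count. The mismatch does not depend on the simulations; it follows from the offset.

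Its size does depend on assumptions. With 20% to 50% of participants abstinent by Week 4 and intensity unchanged, a fall in weekly drinking of about 20% to 50% appears as about 0%, and about 10% to 25% of person-weeks leave the model. A complete miss occurs only in that case. The figures assume that the numerator is drinks and that the offset is logged. They show that the modelled quantity differs from the stated outcome, not that the per-drinking-day estimate is biased.

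Severity: should fix. The documents do not support a claim that Aim 2 as a whole loses its abstinent weeks.

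**What to change.** Replace the consumption sentence so that it specifies:

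- **Outcome:** total drinks in the week, as a count.
- **Exposure:** offset log(days of drinking data observed in that week), normally log 7.
- **Rows:** every observed week enters, with abstinent weeks as zeros.
- **Variance:** allowance for overdispersion, for example a negative binomial mixed model.
- **Drinking days:** not entered as a free covariate.
- **Secondary measure, if wanted:** drinks per drinking day among weeks with drinking, labelled as conditional on drinking.

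This puts the model on the scale of Aim 2 and of the power statement. A two-part model (any drinking in the week, then drinks with a drinking-day offset) would not be enough: someone who goes from five drinking days to one at the same intensity shows no change in either part.

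Cost: one paragraph of the analysis plan and no new data, since drinks per drinking day already requires drinks and drinking days to be recorded. The downside is that the consumption estimate no longer isolates drinking intensity, so one extra secondary model is needed to show it.
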